10. Prior HDAC, DAC, HSP90 inhibitors or valproic acid for the treatment of cancer is allowed.

Exclusion criteria (panobinostat maintenance)

1. Patients who have purely non-secretory multiple myeloma (i.e., the absence of a measurable protein in serum by electrophoresis and immunofixation and the absence of Bence-Jones protein in the urine defined by use of electrophoresis and immunofixation)
2. Prior allogeneic HCT
3. Prior solid organ transplant requiring immunosuppressive therapy
4. Patients who will need valproic acid for any medical condition during the study or within 5 days prior to first panobinostat treatment
5. Impaired cardiac function or clinically significant cardiac diseases, including any one of the following:
 - History or presence of sustained ventricular tachyarrhythmia. (Patients with a history of atrial arrhythmia are eligible but should be discussed with Novartis prior to enrollment)
 - Any history of ventricular fibrillation or torsade de pointes
 - Bradycardia defined as HR < 50 bpm. Patients with pacemakers are eligible if HR \geq 50 bpm.
 - Screening ECG with a QTc > 470 msec
 - Right bundle branch block + left anterior hemiblock (bifascicular block)
 - Patients with myocardial infarction or unstable angina ≤ 12 months prior to starting study drug
 - Other clinically significant heart disease (e.g., CHF NY Heart Association class III or IV, uncontrolled hypertension, history of labile hypertension, or history of poor compliance with an antihypertensive regimen)
4. Patients with diarrhea > CTCAE grade 2
5. Other concurrent severe and/or uncontrolled medical conditions (e.g., uncontrolled diabetes or active or uncontrolled infection) including abnormal laboratory values, that could cause unacceptable safety risks or compromise compliance with the protocol
6. Patients using medications that have a relative risk of prolonging the QT interval or inducing torsade de pointes (see Table 17-1) if treatment cannot be discontinued or switched to a different medication prior to starting study drug
7. Patients who have received targeted agents within 2 weeks or within 5 half-lives of the agent and active metabolites (whichever is longer) and who have not recovered from side effects of those therapies.

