7.5 Other concomitant medications

Patients must be instructed not to take any additional medications (including over-the-counter products) during the trial without prior consultation with the investigator. All medications taken within 30 days of enrollment should be recorded. If concomitant therapy must be added or changed within 30 days of enrollment, the reason and name of the drug/therapy should be recorded. Other concomitant medications are collected once at enrollment (within 30 days of screening).

In general, the use of any concomitant medication/therapies deemed necessary for the care of the patient are allowed, including drugs given prophylactically (e.g. antiemetics) with the following exceptions:

- Any medications listed in [Appendix 17.1.1](#) which may cause QTc prolongation or inducing torsades de pointes should not be used.

- Any medications that have the potential to alter serum electrolytes (e.g., diuretics) should be monitored very closely for electrolyte abnormalities as these can contribute to the risk of QT prolongation and ventricular arrhythmias.
- No other investigational therapy should be given to patients
- No anticancer agents other than the study medications administered as part of this study protocol should be given to patients. If such agents are required for a patient then the patient must first be withdrawn from the study.
- Leukocyte growth factors (e.g. G-CSF and GM-CSF) are not to be administered systematically but may be prescribed by the investigator for severe neutropenia if this is thought to be appropriate.
- Medications known to be substrates of the isoenzyme CYP2D6 should be used with caution with panobinostat as panobinostat can inhibit isoenzyme CYP2D6 at low micromolar ranges. Please refer to [Appendices 17.1.2 and 17.1.3](#) for the lists of CYP2D6 substrates.
- Concomitant use of CYP3A4 inhibitors with panobinostat should be used with caution due to a potential increase in panobinostat exposure during concomitant treatment with these drugs.
- Oral contraceptives are generally metabolized by CYP3A4. Since the induction potential of panobinostat to induce CYP3A4 is unknown, patients who are using oral contraceptives as a method of contraception, and are sexually active, should use another effective contraceptive method.

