16.1 Appendix A: Medications requiring caution for potential drug-drug interactions

16.1.1 Medications which have a risk of causing Torsades de pointes ventricular arrhythmia should be avoided

Patients who are currently receiving treatment of the medications in [Table 17-1](#) and cannot either discontinue from this treatment or switch to an alternative medication prior to enrollment in a panobinostat clinical study, will be excluded from the study. Patients may not begin panobinostat treatment with any of the medications listed in [Table 17-1](#) unless this is discussed with the supporting company (Novartis) and an approval is granted by the supporting company (Novartis). The supporting company (Novartis) may agree to temporarily discontinue panobinostat treatment (e.g., for 72 hours) during administration with these drugs or withheld medications in [Table 17-1](#) for at least 72 hours when panobinostat is to be administered.

NOTE: It is of great importance to avoid combining drugs listed below in [Table 17-1](#) and [Table 17-2](#) (CYP3A inhibitors) especially in the presence of electrolyte abnormalities, notably decreased potassium or magnesium levels commonly associated with diuretic usage.

In general, medications listed in [Table 17-1](#) should be avoided while medications listed in [Tables 17-2](#) and [17-3](#) are to be used with caution when co-administered with panobinostat. Please select the most stringent recommendation for concomitant medications (i.e., to be avoided) which are common among the tables (e.g., erythromycin, clarithromycin)

Table 17-1 Medications which have a risk of causing Torsades de pointes to be avoided

All Class IA antiarrhythmics 
• quinidine• procainamide• disopyramide• any other class IA antiarrhythmic drug
All Class III antiarrhythmics amiodarone sotalol bretylium disopyramide dofetilide ibutilide any other class III antiarrhythmic drug

Antibiotics Macrolide antibiotics* 
• erythromycin• clarithromycin• telithromycin Quinolone antibiotics* sparfloxacin
Antipsychotics thioridazine mesoridazine chlorpromazine pimozide
Antimalarials 
• halofantrine• chloroquine
Miscellaneous drugs 
• arsenic trioxide• astemizole• bepridil• domperidone• levomethadyl• methadone• pentamidine• droperidol

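### Appendix A (16.1.1) opens a company-approval route for torsades-risk drugs that exclusion criterion 6, section 7.5 and the appendix's own first sentence do not allow, and the cut-off date differs too

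*Combined protocol and SAP*

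**What the plan says.** Three places in the combined protocol and SAP govern the drugs in Table 17-1.

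- **Section 6.1.3, exclusion criterion 6.** A patient using such a drug is excluded "if treatment cannot be discontinued or switched to a different medication prior to starting study drug". No company waiver is attached. The opening of 6.1.3 requires every patient to satisfy all inclusion and exclusion criteria.
- **Section 7.5.** Concomitant treatment is generally allowed, with listed exceptions. The first exception is any drug on the appendix list "which may cause QTc prolongation or inducing torsades de pointes should not be used". No waiver is attached here either.
- **Section 16.1.1 (Appendix A).** The first sentence says that patients who can neither stop the drug nor change to another "prior to enrollment in a panobinostat clinical study, will be excluded from the study". The second says patients may not begin panobinostat with a listed drug "unless this is discussed with the supporting company (Novartis) and an approval is granted by the supporting company (Novartis". The third says the company "may agree to temporarily discontinue panobinostat treatment (e.g., for 72 hours) during administration with these drugs", or alternatively that the listed drug may be withheld "for at least 72 hours when panobinostat is to be administered".

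The note below Table 17-1 describes the list as drugs whose risk in combination with panobinostat was judged unacceptable. Section 16.1.1 also contains a tie-break: "Please select the most stringent recommendation for concomitant medications (i.e., to be avoided) which are common among the tables".

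**The concern.** Whether a patient on a torsades-risk drug may enter, and whether such a patient may be dosed, is a QT safety rule. Staff who work from 6.1.3 and 7.5 would turn the patient away or refuse the drug. Staff who read on in 16.1.1 would ask the company for approval and might proceed. Both could claim to be following the protocol.

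An exception would also be hard to see in the data. Section 7.5 and Table 8-1 collect concomitant medications once, at enrollment. Scheduled ECGs are not required beyond cycle 4 unless significant QTcF prolongation has been seen (Tables 8-1 and 8-2). A listed drug started later in the 12 cycles, with company agreement, might leave little trace in the study record.

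**Working it through.** The main check compares texts; the plan has no figure of its own to reproduce. Each kind of patient is taken through the three places.

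| Patient | 6.1.3, criterion 6 | 7.5 | 16.1.1 | Result |
|---|---|---|---|---|
| Can stop or switch before enrollment | Not excluded | Drug no longer in use | Not excluded | Consistent |
| Stops or switches after enrollment but before the first dose | Not excluded | Drug no longer in use at first dose | Excluded by sentence 1, which looks at enrollment | Conflict on cut-off |
| Cannot stop or switch | Excluded | Not to be used | Excluded by sentence 1; may begin with approval under sentence 2 | Conflict, including within 16.1.1 |
| Needs a listed drug during treatment | Not addressed | Not to be used | Possible by company agreement, with one of the two drugs withheld | Conflict |

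**Can the cut-off difference occur in practice?** Table 8-1 allows enrollment from day +45 and a cycle 1 start from day +90. A patient enrolled on day +45 would wait at least 90 − 45 = 45 days, so there is time for a drug to be changed between the two dates.

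**Does anything in the plan settle the conflict?** The tie-break in 16.1.1 applies to drugs that appear in more than one of Tables 17-1 to 17-3. It ranks tables, not sections. No rule of precedence between body and appendix is given. Where 6.1.3 intends a company route it says so: patients with past atrial arrhythmia are eligible but are to be discussed with the company before enrollment. Criterion 6 has no such wording.

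**How much could a pause affect relative dose intensity (RDI)?** Inputs: both schedules dose every other week of a 28-day cycle for 12 cycles (7.1, 7.3); Cohort A takes 20 mg three times a week, Cohort B 10 mg daily for 7 days; RDI is dose received over dose planned (13.1). Assumptions: Cohort A doses on days 1, 3 and 5; the pause lasts 72 hours, which the appendix gives only as an example; it falls where it removes most doses; and missed doses are not made up (7.1).

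- Planned doses, A: 3 × 2 × 12 = 72, or 72 × 20 = 1,440 mg.
- Planned doses, B: 7 × 2 × 12 = 168, or 168 × 10 = 1,680 mg.
- Most doses lost to one pause: 2 in A (48-hour spacing) and 3 in B (24-hour spacing).
- Share of planned drug lost: A 2/72 = 2.8%; B 3/168 = 1.8%. The gap is about 1 percentage point.

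A less well aligned pause removes only 1 dose in Cohort A, and a pause in an off week removes none in either cohort.

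**The case against.** The best defence is that this is ordinary drafting: a short rule in the body, with detail in an appendix to which criterion 6 and section 7.5 both send the reader. Section 16.1.1 says the listed drugs should in general be avoided, its second sentence is framed as a restriction, and nothing there states that approval waives criterion 6. Both options in the third sentence keep the two drugs apart in time. This has some force. Separation in time narrows the clash with 7.5, and the route is not hidden. But 7.5 is worded without exception, and the first two sentences of 16.1.1 give different answers for a patient who cannot stop or switch. Reading the body as controlling leaves the approval sentence with no role for that patient; reading the appendix as controlling overrides criterion 6.

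Several stronger readings are tempting, and the documents do not support them.

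- A reader might infer that criterion 6 excludes everyone on a listed drug. It is conditional: anyone who stops or switches in time is not excluded.
- A reader might infer that the appendix demands a 72-hour panobinostat interruption. The company may agree to one, 72 hours is an example, and withholding the other drug is the alternative.
- A reader might infer that Table 7-2 should carry the pause rule. That table covers toxicity related to study drug, so its silence is not a gap.
- A reader might infer that pauses would distort the tolerability result, because one can remove 2/3 = 67% of a dosing week in Cohort A against 3/7 = 43% in Cohort B. One week is the wrong denominator. Section 13.1 counts completion of 12 cycles whatever the dose modification, section 7.4 requires all interruptions to be recorded, and the loss over the whole course is the 2.8% and 1.8% shown above.

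**Conclusion.** The inconsistency is real and should be corrected. It affects two groups: patients who cannot stop or switch a Table 17-1 drug, who are both excluded and approvable; and patients who need one during treatment, for whom the drug is both ruled out and possible by agreement. A third, smaller conflict is the cut-off, set at first dose in one place and at enrollment in another. All of this rests on the wording alone.

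The documents give no expected number of such patients among the 30, so the count cannot be sized. The statistical consequence of a single pause is small and depends on the assumed Cohort A dosing days and the example length of 72 hours. The case for a change is that a QT safety rule should have one answer; it does not rest on any bias in the primary endpoint. No view is taken here on which clinical rule is right.

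**What to change.** Reconcile exclusion criterion 6, section 7.5 and section 16.1.1 to one rule and one cut-off, and state them identically in all three places. The sponsor decides whether the approval and withholding options are removed from the appendix or carried into 6.1.3 and 7.5, and which date applies. The same amendment can correct a clerical matter: sections 7.5 and 7.5.2 cite Appendices 17.1.1 to 17.1.3, whereas the text is numbered 16.1.1 to 16.1.3. The cost is a wording amendment, with no added visits, tests or patients.

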16.1.2 Medications which are known strong CYP3A4/5 inhibitors to be used with caution

Panobinostat is a substrate of CYP3A4 with minor involvement of CYP2D6, and CYP2C19 in *in vitro* evaluation of its metabolism. Thus, a clinical drug-drug interaction study was conducted using ketoconazole, a strong CYP3A inhibitor, in combination with panobinostat in study [CLBH589B2110](#).

Multiple ketoconazole doses at 400 mg increased C_{max} and AUC of panobinostat by 1.6- and 1.8-fold, respectively, but with no change in T_{max} or half-lives in 14 cancer patients. The less than 2-fold increase in panobinostat AUC upon co-administration of a strong CYP3A inhibitor is considered a weak drug inhibition and not clinically relevant, as panobinostat doses at least 2-fold greater than the evaluated 20 mg dose (i.e., 40 mg and 60 mg) have been safely administered in patients. Thus, co-administration of panobinostat with a moderate or weak CYP3A inhibitor is allowed. However, clinical monitoring of signs and symptoms of panobinostat treatment related adverse events is recommended when long-term (≥ 1 week) concomitant administration of any strong CYP3A inhibitors and panobinostat is medically indicated or investigated in a clinical study.

Patients with impaired liver function (as defined by NCI CTEP criteria)¹ are recommended not to receive panobinostat concomitantly with strong CYP3A inhibitors because potential interaction has not been established in this population.

Table 17-2 Medications which are known strong CYP3A4/5 inhibitors to be used with caution

Macrolide antibiotics* 
• clarithromycin• telithromycin• troleandomycin• erythromycin
Antifungals (azoles)* 
• ketoconazole

 • itraconazole • fluconazole
Antidepressants 
 • nefazodone
Calcium channel blockers* 
 • diltiazem • verapamil
HIV protease inhibitors: 
 • indinavir • nelfinavir • ritonavir • saquinavir
Miscellaneous drugs or products 
 • aprepitant • grapefruit product or juice

* azithromycin, voriconazole, regular orange juice and dihydropyridine calcium channel blockers (e.g. amlodipine, felodipine, nicardipine, nifedipine) are allowed.

This is not a comprehensive list of medications which may inhibit CYP3A4/5. Additional updated versions with moderate and weak CYP3A inhibitors, which are meant to be used as a guide, may be found at the following website: <http://medicine.iupui.edu/clinpharm/DDIs>

16.1.3 Medications which are known CYP2D6 substrates to be used with caution

Panobinostat was also shown to be a CYP2D6 inhibitor (K_i 0.17 μM) *in vitro*. Thus, clinical drug-drug interaction study with panobinostat as CYP2D6 inhibitor and dextromethorphan as CYP2D6 substrate was recently conducted in study [CLBH589B2109](#).

Multiple panobinostat doses increased C_{max} and AUC of dextromethorphan by a mean of 1.8- and 1.6-fold respectively, but with no change in T_{max} in 17 cancer patients. An approximately 2-fold increase in dextromethorphan AUC upon co-administration with panobinostat indicated that *in vivo* CYP2D6 inhibition of panobinostat is weak.

As the study was conducted using a sensitive CYP2D6 substrate which resulted in a weak inhibition, drugs with a large therapeutic index such as anti-emetics, anti-hypertensives, and anti-depressants are generally safe to be co-administered with panobinostat.

Patients should be carefully monitored for potential signs and symptoms of toxicity and may require dose titration or dose reduction of a sensitive CYP2D6 substrate which also have a

narrow therapeutic window (e.g., the ratio of toxicity exposure is \leq 2-fold higher than the efficacious or therapeutic exposure).

Table 17-3 Medications which are known CYP2D6 substrates to be used with caution

Beta blockers (listed below):	Antipsychotics (listed below):
carvedilol	aripiprazole
metoprolol	haloperidol
propafenone	perphenazine
timolol	risperidone
Antidepressants (listed below):	thioridazine
amitriptyline	zuclopenthixol
chlormipramine	amphetamine
desipramine	alprenolol
imipramine	bufuralol
fluoxetine	chloropheniramine
paroxetine	Antiarrhythmics (listed below):
venlafaxine	quinidine
bupropion	lidocaine
duloxetine	mexiletine
Antiemetics (listed below):	propafenone
dolasetron	Others:
ondansetron	oxycodone
metoclopramide	codeine
	hydrocodone
	terbinafine
	promethazine
	tamoxifen
	tramadol

This is not a comprehensive list of CYP2D6 substrates. Additional updated versions of this list, which are meant to be used as a guide, may be found at the following website: <http://medicine.iupui.edu/clinpharm/DDIs>

Reference:

1. Synold TW, Takimoto CH, Doroshow JH, Gandara D, Mani S, Remick SC, Mulkerin DL, Hamilton A, Sharma S, Ramanathan RK, Lenz HJ, Graham M, Longmate J, Kaufman

16.2 Appendix B: Criteria for Symptomatic Multiple Myeloma

All three required:

1. Monoclonal plasma cells in the bone marrow $\geq 10\%$ and/or presence of a biopsy-proven plasmacytoma
2. Monoclonal protein present in the serum and/or urine^a
3. Myeloma-related organ dysfunction (1 or more)^b
 - (C) Calcium elevation in the blood (serum calcium > 10.5 mg/L or upper limit of normal)
 - (R) Renal insufficiency (serum creatinine > 2 mg/dL)
 - (A) Anemia (hemoglobin < 10 g/dL)
 - (B) Lytic bone lesions or osteoporosis^c

*Note: These criteria identify Stage IB and Stages II and III A/B myeloma by Durie-Salmon stage. Stage IA becomes smoldering or indolent myeloma.

^aIf no monoclonal protein is detected (nonsecretory disease), then $\geq 30\%$ monoclonal bone marrow plasma cells and/or a biopsy-proven plasmacytoma required.

^bA variety of other types of end organ dysfunctions can occasionally occur and lead to a need for therapy. Such dysfunction is sufficient to support classification as myeloma if proven to be myeloma-related.

^cIf a solitary (biopsy-proven) plasmacytoma or osteoporosis alone (without fractures) are the sole defining criteria, then $\geq 30\%$ plasma cells are required in the bone marrow.

Reference:

*Myeloma management guidelines: a consensus report from the Scientific Advisors of the International Myeloma Foundation. *The Hematology Journal* 2003;4:379-398

16.3 Appendix C: Uniform Response Reporting Criteria for Multiple Myeloma by the International Myeloma Working Group (IMWG)

Response subcategory	Response Criteria
sCR ¹	
 CR as defined below plus normal FLC ratio and absence of clonal cells in bone marrow by immunohistochemistry or 2- to 4-color flow cytometry
CR ²	
 Negative immunofixation of serum and urine, disappearance of any soft tissue plasmacytomas, and < 5% plasma cells in bone marrow
VGPR ²	
 Serum and urine M-protein detectable by immunofixation but not on electrophoresis or ≥ 90% reduction in serum M-component plus urine M-component < 100 mg per 24 hours
PR	
 ≥ 50% reduction of serum M-protein and reduction in 24 hour urinary M-protein by ≥ 90% or to < 200 mg per 24 hours If the serum and urine M-protein are not measurable, a decrease ≥ 50% in the difference between involved and uninvolved FLC levels is required in place of the M-protein criteria. If serum and urine M-protein and serum FLC are not measurable, and serum free light assay is also not measurable, ≥ 50% reduction in bone marrow plasma cells is required in place of M-protein, provided baseline bone marrow plasma cell percentage was ≥ 30% In addition to the above listed criteria, if present at baseline, ≥ 50% reduction in the size of soft tissue plasmacytomas is also required
SD	
 Not meeting criteria for CR, VGPR, PR, or PD
PD ¹	
 Increase of 25% from lowest response value in any of the following: 
 - Serum M-component (absolute increase must be ≥ 0.5 g/dL) - Urine M-component (absolute increase must be ≥ 200 mg/24 h) - Only in patients without measurable serum and urine M-protein levels: the difference between involved and uninvolved FLC levels (absolute increase must be > 10 mg/dL) - Only in patients without measurable serum and urine M protein levels and without measurable disease by FLC levels, bone marrow plasma cell percentage (absolute percentage must be ≥ 10%) - Definite development of new bone lesions or soft tissue plasmacytomas or definite increase in the size of existing bone lesions or soft tissue plasmacytomas - Development of hypercalcemia (corrected serum calcium > 11.5 mg/dL) that can be attributed solely to the plasma cell proliferative disorder

Footnotes:

- 1: Clarifications to IMWG criteria for coding PD: Bone marrow criteria for PD are to be used only in patients without measurable disease by M protein and by FLC levels; “25% increase” refers to M protein, FLC, and bone marrow results, and does not refer to bone lesions, soft tissue plasmacytomas, or hypercalcemia and the “lowest response value” does not need to be a confirmed value.
- 2: Clarifications to IMGW criteria for coding CR and VGPR in patients in whom the only measurable disease is by serum FLC levels: CR in such patients indicates a normal FLC ratio of 0.26 to 1.65 in addition to CR criteria listed above. VGPR in such patients requires a > 90% decrease in the difference between involved and uninvolved FLC levels.

Reference:

